### **8.4.2 Serious Adverse Event Reporting**

Every SAE, regardless of suspected causality, occurring after the patient has provided main informed consent and until at least 30 days after the patient has stopped study treatment must be reported to the Sponsor within 24 hours of site awareness.

Any SAE experienced after this 30-day period should only be reported to the Sponsor if the investigator suspects a causal relationship to the study treatment. Recurrent episodes, complications, or progression

of the initial SAE must be reported as follow-up to the original episode within 24 hours of the investigator receiving the follow-up information.

Information about all SAEs will be recorded on the Serious Adverse Event Report Form.

All SAEs will be followed until satisfactory resolution or until the site investigator deems the event to be chronic or the adherence to be stable. Other supporting documentation of the event may be requested by the study sponsor and should be provided as soon as possible. The study sponsor will be responsible for notifying Health Authorities of any unexpected fatal or life-threatening suspected adverse reaction as soon as possible but in no case later than 7 calendar days after the sponsor's initial receipt of the information.

Suspected Unexpected Serious Adverse Reactions (SUSARs) will be collected and reported to the competent authorities and relevant ethics committees in accordance with Directive 2001/20/EC or as per national regulatory requirements in participating countries.

### **8.4.3 Events of Special Interest**

Safety events of special interest include, but are not limited to:

- Secondary Primary Malignancies
- Infusion Related Reactions
- Medication Error, intercepted medication error or potential medication error (with or without patient exposure to IMP, e.g., product name confusion, product label confusion, intercepted prescribing or dispensing errors)
- Abuse/Misuse/Overdose
- Occupational Exposure
- Drug-Drug Interaction
- Suspected Transmission of Infectious Agents
- Exposure from breastfeeding
- Unexpected therapeutic benefit or clinical benefit
- Inadvertent or accidental exposure

All events of special interest should be especially monitored and reported to the sponsor as SAEs and within 24 hours of site awareness, even if considered non-serious and regardless whether or not an (S)AE occurred. All of the events of special interest should be recorded on the eCRF.

### **8.4.4 Pregnancy**

A female patient will be instructed immediately to inform the investigator if she becomes pregnant during the study. The investigator shall report all pregnancies within 24 hours to the sponsor using the Pregnancy Reporting Form. Monitoring of the patient should continue until conclusion of the pregnancy. Pregnancies occurring up to 90 days after the completion of the study medication must also be reported to the investigator.

There are no human or animal data to assess the risk of daratumumab use during pregnancy. IgG1 monoclonal antibodies are known to cross the placenta after the first trimester of pregnancy. Therefore, daratumumab should not be used during pregnancy unless the benefit of treatment to the woman is considered to outweigh the potential risks to the fetus. The investigator will therefore inform the subject of the potential risks to the fetus and discuss with the Sponsor as well as the subject if it is in the subject's best interest to continue or stop treatment with daratumumab.

The effect of daratumumab on sperm is unknown. Therefore, pregnancy occurring in the partner of a male patient participating in the study should also be reported by the investigator within 24 hours of awareness to the sponsor by using the Pregnancy Reporting Form..

#### **8.4.5 Product Quality Complaints**

A product quality complaint (PQC) is defined as any suspicion of a product defect related to manufacturing, labeling, or packaging, i.e. any dissatisfaction relative to the identity, quality, durability, or reliability of a product, including its labeling or package integrity. A PQC may have an effect on the safety and efficacy of the product; therefore the timely, accurate, and complete reporting and analysis of PQC information are crucial for the protection of subjects, Investigators, and the Sponsor.

All PQCs must be reported to the Sponsor using the PQC form within 24 hours upon awareness, regardless if the relevant defect is combined with a (S)AE or not. Where possible, a sample of the suspected product should be maintained for further investigation if requested by the Sponsor.

#### **8.4.6 Annual Safety Report**

An Annual Safety Report will be submitted to the Competent Authorities and Ethics Committees once a year, according to the relevant local regulations.

### **8.5 Safety Oversight**

Safety data will be reviewed by the study Scientific Committee approximately every 6 months (after first randomized patient started study treatment).

## **9. Clinical Monitoring**

Clinical site monitoring will be conducted to ensure that the rights and well-being of human subjects are protected, that the reported trial data are accurate, complete, and verifiable, and that the conduct of the trial complies with the currently approved protocol, with GCP, and with applicable regulatory requirements.

Monitoring for this study will be performed by a Contract Research Organization (CRO).

Details of clinical site monitoring are documented in a Clinical Monitoring Plan (CMP). The CMP describes in detail who will conduct the monitoring, at what frequency monitoring will be done, at what level of detail monitoring will be performed, and the distribution of monitoring reports.

Independent audits may be conducted to ensure monitoring practices are performed consistently across all participating sites and that monitors are following the CMP.

## **10. Statistical considerations**

### **10.1 Statistical and Analytical Plans**

The primary analysis will be performed when the targeted number of events required for the primary analysis has been reached.

## 10.2 Statistical Hypotheses

The primary efficacy endpoint is PFS as assessed by the Investigator.

The expected median PFS with daratumumab treatment in the SIRIUS study was 5.6 months in the patients who received daratumumab at the dose of 16 mg/kg.

In order to test at  $\alpha=0.05$  the null hypothesis that the PFS is less than 3 months versus the alternative hypothesis that PFS is at least 5 months with a power of 90%, 34 patients must be included in the study. This calculation assumes exponential survival curves, an accrual time of 18 months and a length of follow up period of 30 months. Assuming a drop-out rate of about 10%, 38 patients are needed.

The distribution of PFS will be estimated using the Kaplan-Meier method. The median PFS along with 95% confidence intervals will be presented (see Section 10.4.2).

The analysis will be performed when at least 20 PFS events have been documented.

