## 10.4 Description of Statistical Methods

### 10.4.1 General Approach

All data collected in this study will be listed and summarized as appropriate as described below. Data from all sites will be pooled and summarized.

Continuous data will be summarized by mean, standard deviation, median, first and third quartiles, minimum and maximum. Categorical data will be presented by absolute and relative frequencies (n and %) or contingency tables.

One-sided alpha level 0.025 will be considered. No alpha level adjustment will be carried out for primary and secondary outcome variables.

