### **Progression Free Survival (PFS)**

Progression free survival is defined as the time, in months, from treatment initiation (Cycle 1 , day 1) to the date of the first documented disease progression or death due to any cause, whichever comes first. Clinical deterioration will not be considered progression. For subjects who neither progress nor die, the survival time will be censored at the date of their last disease assessment. For subjects who start a new anti-tumor treatment, survival time will be censored at the date of the start of the new treatment.

The PFS function will be estimated using the Kaplan-Meier product-limit method. Median and two-sided confidence intervals (CI) for median PFS will be computed by and Kaplan-Meier plots of PFS will be presented.

Absolute frequencies and proportions of patients with disease progression or all-cause death will also be provided.

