#### **10.4.7.2 Efficacy Review**

No formal efficacy review is planned.

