### **10.4.9 Multiple Comparison/Multiplicity**

Unless stated otherwise, one-sided alpha level 0.025 will be considered. No alpha level adjustment will be carried out for primary and secondary endpoints.

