## 10.5 Sample Size

The calculations were based on previous data for daratumumab in patients with relapse or refractory myeloma. The median PFS with daratumumab treatment in the SIRIUS study was 5.6 months in patients who received daratumumab at the dose of 16 mg/kg.

In order to test at  $\alpha=0.05$  the null hypothesis that the PFS is less than 3 months versus the alternative hypothesis that PFS is at least 5 months with a power of 90%, 34 patients must be included in the study. This calculation assumes exponential survival curves, an accrual time of 18 months and a length of follow up period of 30 months. Assuming a drop-out rate of about 10%, 38 patients are needed.

Sample size was computed by “SWOG One arm survival sample size and power” ([www.swogstat.org/stat/public/one\\_survival.htm](http://www.swogstat.org/stat/public/one_survival.htm))

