### **13.2 Institutional Review Board (IRB)/independent Ethics Committee (IEC) and competent authority**

The protocol, informed consent form(s), recruitment materials, and all participant materials will be submitted to the relevant IRB/EC and Competent Authority (CA) for review and approval. Approval of both the protocol and the consent form must be obtained before any participant is enrolled. Any amendment to the protocol will require review and approval by the IRB/EC and or CA before the changes are implemented to the study. All changes to the consent form will be IRB/EC and/or CA approved; a determination will be made regarding whether previously consented participants need to be re-consented.

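### The primary PFS analysis may be run at 20 events, but the stated 90% power needs about 33; at 20 events power is about 74% at one-sided 0.05.

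*Protocol*

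**What the plan says.** Protocol 10.2 and 10.5 and SAP 6.4.2 give the same sizing: alpha 0.05 with no sidedness stated, null median PFS 3 months, alternative 5 months, 90% power, 34 patients, raised to 38 for about 10% drop-out. On the time frame, Protocol 10.5 states: "This calculation assumes exponential survival curves, an accrual time of 18 months and a length of follow up period of 30 months".

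Protocol 10.1 sets the timing in general terms: "The primary analysis will be performed when the targeted number of events required for the primary analysis has been reached". The only event count in either document is in Protocol 10.2, and SAP 6.6 repeats it: "The analysis will be performed when at least 20 PFS events have been documented".

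The analysis sections use a different alpha. Protocol 10.4.1 says "One-sided alpha level 0.025 will be considered", as does SAP 6.6, and Protocol 10.4.9 says "Unless stated otherwise, one-sided alpha level 0.025 will be considered". For the analysis itself, Protocol 10.4.2 says "The PFS function will be estimated using the Kaplan-Meier product-limit method" and adds a confidence interval for the median. No test of the 3-month null is named. On interim looks, Protocol 10.4.7.2 says "No formal efficacy review is planned", and SAP 6.5.5 marks interim analysis as not applicable.

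**The concern.** In a time-to-event design with exponential curves, power is governed by the number of events. Protocol 10.1 implies that a required number of events exists, and 20 is the only candidate offered. If 20 is that number, it does not support the 90% power claimed in the same section.

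Two things are at stake. First, an analysis at the permitted minimum would carry a type II error of about 26% instead of 10%. Second, any cut from event 20 to the end of the study complies with the plan. PFS is investigator-assessed in an open-label single-arm trial, so the results can be seen as they accumulate, and the date of the primary analysis should not be left to choice. An early cut could also fall before enrolment is complete and leave out some of the 38 planned patients.

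**Working it through.** **Inputs.** From Protocol 10.2 and 10.5: medians 3 and 5 months, exponential curves, 90% power, alpha 0.05, 18 months of accrual, 30 months of follow-up, 10% drop-out. From Protocol 4.1: 24 months of accrual and 37 months in total. Uniform accrual is an assumption; the documents give no accrual pattern.

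**1. Reproduce the 34 patients.** For a one-sample exponential test on the log-hazard scale, the events needed are d = [(z_alpha + z_power) / ln(5/3)]², with ln(5/3) = 0.5108 and its square 0.2609.

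- One-sided 0.05: (1.645 + 1.2816)² / 0.2609 = 32.8, so 33 events.
- One-sided 0.025, the same as two-sided 0.05: (1.960 + 1.2816)² / 0.2609 = 40.3, so 41 events.

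With hazard λ = ln2/5, accrual A = 18 and follow-up F = 30, the probability of an event is 1 − [exp(−λF) − exp(−λ(A+F))] / (λA) = 0.994. Then N = 32.8 / 0.994 = 33.0 (33.01 before rounding, so 34). The cube-root form of the test gives 33.8, also 34. Inflation gives 34 / 0.9 = 37.8, so 38. Two-sided 0.05 gives 40.5 to 46.6 patients and does not reproduce 34. The stated sample size is therefore correct for one-sided 0.05, and it rests on 34 × 0.994 = 33.8 events.

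**2. Power by number of events.** The log-hazard form is Φ(√d × 0.5108 − z_alpha). The exact form uses total time at risk: power is P(χ² with 2d df > 0.6 × critical value), where 0.6 = 3/5 is the hazard ratio.

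| Events | Alpha (one-sided) | Log-hazard | Exact | Cube-root |
|---|---|---|---|---|
| 20 | 0.05 | 73.9% | 75.8% | 70.6% |
| 20 | 0.025 | 62.7% | 66.8% | 56.6% |
| 33 | 0.05 | 90.1% | 90.3% | 89.4% |
| 33 | 0.025 | 83.5% | 85.0% | 80.9% |
| 34 | 0.05 | 90.9% | 91.0% | 90.3% |

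For d = 20 at one-sided 0.05: 4.472 × 0.5108 − 1.645 = 0.639, and Φ(0.639) = 0.739.

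**3. When event 20 would occur.** With 38 patients, median 5 months and uniform accrual over 24 months, expected events at month t ≤ 24 are (38/24) × [t − (1 − exp(−λt))/λ]. This reaches 20 at month 19.4, when 19.4 × 38/24 ≈ 31 patients are enrolled. With a drop-out hazard of λ/9 (10% lost before an event) it is month 20.2, with about 32 enrolled. Simulated probability that event 20 precedes the last enrolment:

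| Accrual | No drop-out | 10% drop-out |
|---|---|---|
| Uniform, 24 months | 99% | 95% |
| Uniform, 18 months | 89% | 78% |
| Linearly rising, 24 months | 70% | 56% |
| Linearly rising, 18 months | 33% | 23% |

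**4. Whether 33 events are attainable.** With uniform 24-month accrual, about 36 events are expected by month 37 without drop-out and 33 with 10% drop-out. At least 33 are reached by then in 99% and 61% of simulations.

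**5. A rule of completed enrolment and 33 events, or month 37 if earlier.** Simulated with uniform 24-month accrual and 10% drop-out: mean 32.2 events, median cut at month 34.4, exact-test power 0.90 at one-sided 0.05 and 0.85 at 0.025. Type I error was between 0.049 and 0.053, and between 0.024 and 0.027, in separate simulations, which is at or near nominal.

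**The case against.** The strongest reply is that no printed number is wrong. The trial is sized by patients, 34 and 38 both reproduce, and 20 is only a floor. A mature analysis at 34 to 36 events satisfies it with 91% to 92% power at one-sided 0.05. The primary analysis is on the FAS, 34 patients must be included, and no efficacy interim is planned, so a cut with enrolment still open fits poorly with the rest of the plan. This is fair as a reading of intent, but none of these provisions forbids a cut at event 20, and a trigger that permits both 74% and 92% power does not secure 90%.

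The power figures also depend on a test that the analysis sections never name. That stands as a condition on the figures. It does not remove the problem, because the sample size is justified by just such a test, and an estimate of the median is also less precise at 20 events.

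The timing figures depend on accrual. That stands too: with rising accrual over 18 months, event 20 would more often fall after enrolment ends. The shortfall in power does not depend on accrual.

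Finally, 33 events do not give 90% at one-sided 0.025, and with 10% drop-out they are missed by month 37 in about 39% of simulations. Both are true, so the fix needs an end-of-study clause and a power statement matched to the chosen alpha.

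**Conclusion.** The concern holds. The only trigger in the plan permits the primary analysis at 20 events, whereas the stated 90% power corresponds to about 33 (34 under the cube-root form). At the permitted minimum, power is 71% to 76% at one-sided 0.05 and 57% to 67% at one-sided 0.025. These figures assume exponential PFS, true medians of 3 and 5 months, and a one-sample parametric test.

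The plan does not require a cut at 20; the defect is that it allows one without explanation and fixes no later date. That such a cut would leave out planned patients is likely under uniform accrual but not under every pattern. At one-sided 0.025, 90% power would need 41 events on the log-hazard form, more than the 38 patients planned, so the power claim and the analysis alpha must be reconciled whatever trigger is chosen. This should be settled before the data cut.

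**What to change.** In Protocol 10.2 and SAP 6.6, replace the trigger with wording such as: *The primary analysis will be performed after enrolment is complete and 33 PFS events have been documented, or at the end of study (month 37) if that comes first.* Refer to that number in Protocol 10.1. The SAP still describes a 30-month study (18 + 12 months), so its duration should be brought into line with the protocol's 37 months at the same time.

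State one alpha, with its sidedness, for the primary test, name the test, and give the power that matches: about 90% at one-sided 0.05, or about 84% (exact 85%) at one-sided 0.025.

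If 20 events is kept for a reason, state the reason and replace the 90% with the power at 20 events for the chosen alpha.

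**Cost.** Two sentences in each document and no extra patients. The protocol change is an amendment: "Any amendment to the protocol will require review and approval by the IRB/EC and or CA before the changes are implemented to the study". Compared with a cut at 20 events under uniform 24-month accrual, the primary analysis moves about 10 months later without drop-out (to about month 29 to 30) and about 14 to 15 months later with 10% drop-out (median month 34). Both fall within the 37-month study. With 10% drop-out the end-of-study clause would apply in roughly 4 of 10 cases.

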## 10.3 Analysis Datasets

### Full Analysis Set

The Full Analysis Set (FAS) comprises all patients to whom study treatment has been assigned according to the intent to treat principle.

### Per Protocol Set

The Per-Protocol Set (PPS) consists of a subset of patients in the FAS who received at least one dose of the study drug and had no major protocol deviation. Protocol deviations leading to exclusion from the PPS will be defined in the Statistical Analysis Plan.

### Safety Set

The Safety Set consists of all patients who received at least one dose of study treatment. Patients who have been randomized and did not take at least one dose of study treatment will not be included in the safety set. Patients will be analyzed according to the study treatment they actually received.

## 10.4 Description of Statistical Methods

### 10.4.1 General Approach

All data collected in this study will be listed and summarized as appropriate as described below. Data from all sites will be pooled and summarized.

Continuous data will be summarized by mean, standard deviation, median, first and third quartiles, minimum and maximum. Categorical data will be presented by absolute and relative frequencies (n and %) or contingency tables.

One-sided alpha level 0.025 will be considered. No alpha level adjustment will be carried out for primary and secondary outcome variables.

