**Study Duration:**

The maximum duration of the study is 37 months considering an accrual period of 24 months and a follow-up of the last patient for 13 months.

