6.4.2 Sample Size and Power Calculations

The calculations were based on previous data for daratumumab in patients with relapse or refractory myeloma. The median Progression Free Survival (PFS) with daratumumab treatment in the SIRIUS study was 5.6 months in patients who received daratumumab at the dose of 16 mg/kg.

Health Data Specialists	
DARE (EAE-2017/MM02)- Statistical Analysis Plan	Version: 1.0 EN
Author: GC, Reviewer: MS, Quality Assurance: GK	Date: 02-02-2018

In order to test at $\alpha=0.05$ the null hypothesis that the PFS is less than 3 months versus the alternative hypothesis that PFS is at least 5 months with a power of 90%, 34 patients must be included in the study. This calculation assumes exponential survival curves, an accrual time of 18 months and a length of follow up period of 30 months. Assuming a drop-out rate of about 10%, 38 patients are needed.

Sample size was computed by “SWOG One arm survival sample size and power” (www.swogstat.org/stat/public/one_survival.htm)

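### The trial is sized at alpha 0.05 with no sidedness, but the analysis sections set one-sided 0.025, where 34 evaluable patients give about 81–86% power, not 90%

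*Protocol*

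**What the plan says.** **Sizing.** Protocol 10.2 and 10.5 and SAP 6.4.2 set alpha at 0.05, without saying one-sided or two-sided, for "the null hypothesis that the PFS is less than 3 months versus the alternative hypothesis that PFS is at least 5 months". Protocol 10.5 gives the result as "the alternative hypothesis that PFS is at least 5 months with a power of 90%, 34 patients must be included in the study", raised to 38 for about 10% drop-out. On timing it says: "This calculation assumes exponential survival curves, an accrual time of 18 months and a length of follow up period of 30 months".

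**Analysis level.** Protocol 10.4.1 says "One-sided alpha level 0.025 will be considered", and its next sentence rules out alpha adjustment for primary and secondary outcomes. SAP 6.6 repeats both sentences. Protocol 10.4.9 has a softer form: "Unless stated otherwise, one-sided alpha level 0.025 will be considered".

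**Reporting and timing.** For PFS, Protocol 10.2 says "The median PFS along with 95% confidence intervals will be presented" and "The analysis will be performed when at least 20 PFS events have been documented". The Protocol Summary now gives the study duration "considering an accrual period of 24 months and a follow-up of the last patient for 13 months".

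**The concern.** The plan gives two significance levels for one primary hypothesis, and the sample size fits only one reading of them. If 0.05 in the sizing text means one-sided, it conflicts with the declared one-sided 0.025. If it means two-sided, the levels agree, but 34 patients should then fall short of 90% power.

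PFS is the only primary endpoint of a single-arm trial. A result that excludes a 3-month median at one-sided 5% but not at 2.5% would be a success under one section and a failure under another. If the level is settled only after the data are seen, the false-positive rate has been chosen post hoc.

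**Working it through.** **Inputs.** Medians 3 and 5 months, exponential survival, 34 evaluable patients, 18 months' accrual and 30 months' follow-up (Protocol 10.5); 24 and 13 months (Protocol Summary). Assumptions: accrual is uniform and the 3 and 5 months are medians. The documents do not give the formula of the cited calculator, so three standard one-sample methods were used.

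**Hazards.** λ0 = ln2/3 = 0.2310; λ1 = ln2/5 = 0.1386; ln(λ0/λ1) = ln(5/3) = 0.5108.

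**Event probability** with accrual A and follow-up F: p = 1 − (e^(−λF) − e^(−λ(A+F)))/(λA).
- 18+30: p0 = 0.9998, p1 = 0.9943, so 34 patients give 33.8 events under the alternative.
- 24+13: p0 = 0.9911, p1 = 0.9522, so 32.4 events.

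**Power formulas.**
- Log-hazard: Φ[(ln(5/3) − z/√(n·p0))·√(n·p1)].
- Cube-root: the same construction on λ^(1/3), with standard error λ^(1/3)/(3√(n·p)).
- Exact: P(χ² on 2d df > 0.6 × its upper-alpha critical value), with d = n·p1 events.

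**The plan's own figure (one-sided 0.05, 18+30).** Log-hazard: (0.5108 − 1.645/√33.99)·√33.80 = 1.330, so power is 90.8%. Cube-root gives 90.2% and exact gives 90.9%. The n for 90% is 32.9 by log-hazard, 33.8 by cube-root and 32.7 by exact, so 33 or 34 after rounding up. Only cube-root rounds to the stated 34. Then 34/0.9 = 37.8, which rounds to 38. The figures reproduce.

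**At one-sided 0.025 (same as two-sided 0.05), 18+30.** Log-hazard: (0.5108 − 1.960/√33.99)·√33.80 = 1.015, so power is 84.5%. Cube-root gives 82.1%. Exact gives 85.7%, or 85.9% if all 34 patients have an event.

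| 34 evaluable patients | Log-hazard | Cube-root | Exact |
|---|---|---|---|
| One-sided 0.05, 18+30 | 90.8% | 90.2% | 90.9% |
| One-sided 0.05, 24+13 | 90.2% | 89.6% | 89.9% |
| One-sided 0.025, 18+30 | 84.5% | 82.1% | 85.7% |
| One-sided 0.025, 24+13 | 83.8% | 81.4% | 84.4% |
| n for 90% at 0.025, 18+30 | 40.4 | 42.0 | 39.5 |
| n for 90% at 0.025, 24+13 | 41.3 | 42.9 | 41.2 |

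**Sensitivity.** SAP sections 4 and 6.2 describe 30 months as the total duration (18+12). If the sizing text meant that, power at 0.025 is 83.4% (log-hazard), 80.9% (cube-root) or 83.6% (exact), and the conclusion is the same.

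**At exactly 20 events, one-sided 0.025.** Power is 63% (log-hazard), 67% (exact) or 57% (cube-root).

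**The case against.** The strongest reply is that the Protocol is coherent as it stands. Section 10.4.9 sets 0.025 as a default that gives way to specific statements. Sections 10.2 and 10.5 make a specific statement, alpha 0.05, for one directionally worded hypothesis. On that reading nothing is miscalculated and only the word one-sided is missing. This is a fair reading, and under it the 90% stands. But the plan does not require it: the sizing text never names a one-sided 0.05 test, and 10.4.1 and SAP 6.6 carry no exception.

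Two related points have some force. The sentence after the 0.025 statement in 10.4.1 concerns multiplicity adjustment, so it does not itself say that the PFS null is tested at 0.025. And the planned PFS analysis is a Kaplan–Meier median with a two-sided interval, with no test of the 3-month null named, so the 95% interval supports 0.025 without proving it. Both show that the operative level is unclear; neither shows that it is 0.05.

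It can also be said that the primary analysis uses the full analysis set, so drop-outs still contribute as censored patients. If all 38 were evaluable under 18+30, power at 0.025 would be 86.6–89.0%. That is an upper bound and is still below 90%.

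Finally, 20 events is a minimum, not the planned count. So the 20-event power is a caveat to state beside the power figure, not a second error.

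**Conclusion.** The inconsistency is real. The stated 34 patients and 90% power are correct at one-sided 0.05, which the plan does not declare. At the level it does declare, power with 34 evaluable patients is about 81–86%, a shortfall of about 4–9 points, and 90% would need about 40–43 evaluable patients. Which statement is wrong, the analysis alpha or the power, depends on the sponsor's intention and cannot be settled from the documents.

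The figures rest on exponential survival, uniform accrual, a test at full event maturity (about 32–34 events) and the 3 and 5 months being medians. They vary by a few points with the test used, but all three methods and all the timelines in the documents lead to the same conclusion. This should be fixed because it affects how the primary result is read; it does not bear on patient safety.

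**What to change.** Leave the sample size as it is. State one alpha with its sidedness in Protocol 10.2, 10.4.1, 10.4.9 and 10.5 and in SAP 6.4.2 and 6.6, then take one of two routes:

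- **Keep one-sided 0.025** (consistent with the 95% interval). Restate the power at 34 evaluable patients, naming the test or formula and the accrual and follow-up assumed. At 24+13 months this is about 84% by log-hazard or 81% by cube-root, within an overall range of 81–86%.
- **Use one-sided 0.05 for the PFS hypothesis.** Write it as an explicit exception in 10.4.1, 10.4.9 and SAP 6.6. The 90% then stands (89.6–90.2% under 24+13).

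Either way, add one sentence saying that the power refers to the exponential one-sample test at about 32–34 events, not to an analysis run at the 20-event minimum.

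The cost is wording only, plus the consequence of the choice: the stated power falls by about 4–9 points, or the declared one-sided type I error for PFS becomes 5%.
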